## **9.2 Trial Performance**

### **9.2.1 Intervention Integrity**

There are two major threats to the integrity of the interventions. First, counselors may not deliver the interventions as intended. As described in sections 6.2. and 6.3.3, two procedures will be used to minimize this threat. Both interventions will be manual driven, and the therapists will receive 20 hours of training in conducting the interventions. All intervention sessions will be audiotaped. The Lead Investigator (or designee), Study Project Manager, clinical supervisor, and/or the CTP Site Coordinator will review a portion of each counselor's audiotapes. Therapists will receive regular supervision, including feedback on deviations from the manual.

Second, there is a potential threat of contamination between the interventions. Since HE is a component of the SSB intervention, contamination from HE to SSB is not an issue. However, there are 3 potential sources of contamination from SSB to HE. First, the study intervention counselors, trained in both interventions, may deviate from training guidelines, to refrain from introducing SSB material in HE sessions, and do so. In order to minimize this deviation, HE has been designed with ample didactic material that there is little time to introduce SSB problem-solving or role play. In addition, as described in section 6.3.3, rigorous procedures for intervention supervision, including audiotape review and feedback, will serve to minimize this threat. Second, subjects in SSB intervention may share SSB material with HE subjects. Third, HE subjects may be exposed to SSB material through non-study-related sources – like street outreach workers or media campaigns. To monitor these potential sources of contamination, subjects will be asked to complete an intervention fidelity questionnaire at each follow up assessment -- to determine if they have been exposed to elements of either intervention. Counselors will be asked to complete an intervention fidelity questionnaire after each intervention session – to document the content and the activities of the sessions they conducted.

[figure not shown]
### **9.2.2 Data integrity**

The Long Island Node Data Management Center (DMC) will coordinate data management activities and be responsible for oversight of data integrity. Rigorous procedures for assuring data integrity are detailed in Sections 15.0 to 15.5.

## **9.3 Trial Efficacy**

In view of the limited (i.e. single-study) evidence of the efficacy of this intervention, only within a methadone maintenance treatment program, we plan to conduct an interim analysis, primarily for futility. This plan is described in Section 11.8.

### **Figure 3 AE / SAE Reporting Flow Chart**

## **10.0 Departure From Protocol**

All departures from protocol will be documented following appropriate CTN SOP forms, as well as Node-specific IRB reporting requirements.

## **11.0 Statistical Analyses**

### **11.1 Objectives of Analysis**

The proposed trial is intended to test the effectiveness of SSB intervention, as compared to that of single-session HIV education. There will be one primary outcome: number of unprotected penetrative (vaginal or anal) intercourse occasions during the 3-month and 6-month follow-up periods. Secondary outcomes will include: proportion of drugs or alcohol with sex occasions (of all sex occasions); proportion of unprotected sex occasions (of all sex occasions); perceived self-efficacy to carry out safer sex; carrying condoms; and gender role beliefs.

### **11.2 Sample Size and Statistical Power**

The sample size is determined to ensure sufficient power (at least 80%) of a significance test (with level of significance  $\alpha=0.05$ ) to detect a clinically meaningful intervention effect with respect to the primary outcome measure (number of unprotected penetrative sex occasions).

The study design is a stratified cluster randomization trial (Donner and Klar, 2000). The intervention groups constitute the clusters. Each intervention group will consist of approximately 3 to 8 women depending on the number of eligible subjects recruited in the fixed time interval of 4 weeks. The strata are the 12 CTP sites – in which 40 participants per stratum will be enrolled. Thus, within each stratum, 5 to 10 clusters will be randomized in a balanced fashion to the two interventions. Below is presented the power of the test for comparison of the two interventions subject to these design and recruitment restrictions. Tables 1 and 2 were developed for different counts of CTPs (with the number of subjects per CTP fixed at 40). The two tables corresponding to 12 CTPs (and shown in the protocol) resulted in power values that were closest to our goals.

The power analysis for the stratified cluster randomization trial is based on a test statistic proposed by Liu & Liang (1997). The test statistic is based on generalized estimating equation (GEE). The power analysis takes into account the fact that data are correlated (repeated observations on a subject, the measurements of subjects belonging to the same intervention group (cluster) and from the same CTP (strata) and that the outcome follows a non-normal distribution.

The test statistic is actually a quasi-score statistic based on the generalized estimating equation. The asymptotic distributions of the test statistic under  $H_0$  and  $H_1$  are both known. In the analysis we assume the outcome (the number of unprotected sex occasions) follows a Poisson distribution with the marginal mean being a function of the intervention. In this case, under the null hypothesis the test statistic converges to Chi-square distribution with 1 degree of freedom. Under the  $H_1$ , the test statistic converges to non-central Chi-square distribution with 1 degree of freedom. After we specify the parameters in the linear predictor for the mean and in the covariance matrix of the outcome (that is, the working correlation matrix which does not have to be necessarily

exactly correct), we can compute the non-central parameter and thus determine the power of the test.

Power of the test for difference between the two interventions with respect to number of unprotected sex occasions is computed for a range a values of the difference and the associated covariance parameters. As described in Section 8.4.2: Sexual and Sexual Risk Behavior Assessment, following state-of-the-art practices in HIV risk behavior intervention research, our primary outcome variable is number of unprotected sex occasions in the past 3 months. For purposes of our sample size and statistical power considerations, we have drawn on the HIV prevention intervention findings, among a comparable population of at-risk-for-HIV, inner city women, of Ehrhardt et. al. (2002). They reported an average of 17 unprotected sexual occasions in the 3 months prior to intervention in their sample. In our examination of differences between the two intervention conditions of our study, we have considered 3 levels of differences from this average. In particular, we have considered: (1) A difference of 2 unprotected sex occasions, or 15 versus 17; (2) A difference of 1.5, of 15.5 versus 17; and (3) a difference of 1, or 16 versus 17. In as much as a single occasion of unprotected sex can result in HIV infection, these differences are considered clinically significant. It should be noted that Ehrhardt et al. (2002) article did not present actual averages for their 3 intervention conditions. We have obtained unpublished averages from the authors, as follows: (1) Baseline: Control (0 intervention sessions):17.4; 4-session intervention: 13.7; 8-session intervention: 20.9; and (2) Three-month follow-up: Control: 19.5; 4-session intervention: 13.17; 8-session: 11.23.

Difference in the number of the of unprotected sex occasions:

- 1) Experimental intervention mean=15, control intervention mean=17
- 2) Experimental intervention mean=15.5, control intervention mean=17
- 3) Experimental intervention mean=16, control intervention mean=17

Parameters related to the covariance:

The correlation between repeated observations on a subject is  $\rho_1$ . The correlation between subjects in the same therapeutic group (cluster) is  $\rho_2$  and  $\rho_2 \leq \rho_1$ . The correlation between subjects from different therapeutic groups within the same CTP (strata) is  $\rho_3$  and  $\rho_3 \leq \rho_2$ .

- 1) within subject correlation:  $\rho_1 = 0.4, 0.6, 0.8$
- 2) within therapeutic group (cluster) correlation:  $\rho_2 = 0.15, 0.1$
- 3) within site (strata) correlation:  $\rho_3 = 0.1, 0.05$

The variance parameters are determined by the means described above, since the outcomes are Poisson random variables. When specifying the variances, there are two choices:

- 1) just Poisson variance, and
- 2) extra variation due to the effect of cluster and strata, i.e. over-dispersion.

Suppose that conditional on cluster and strata the variance of the outcome is a Poisson variance, for example, the variance of the outcome (X) in the control intervention with mean 17 is  $\text{Var}(X|\text{cluster, strata})=17$ . Then the marginal variance of the outcome is over-dispersed to  $\text{Var}(X)=17/(1-\rho_2-\rho_3)$ . For the experimental intervention group with mean 15 the over-dispersion is  $15/(1-\rho_2-\rho_3)$ . Presented are results for Poisson and for over-dispersed Poisson variation.

As explained above, the intervention groups' size will vary between 3 and 8; and therefore the number of clusters (intervention groups) within strata (CTP) will be between 10 and 5. From a statistical perspective it is advantageous to have small clusters (intervention groups of size 4) and many clusters per strata (here 10 clusters for a total of 40 subjects per strata (CTP)); such design will have higher power than a design where the clusters will be large but the number of clusters per strata will be small as it is when there are 8 subjects per intervention group for a total of 5 intervention groups per CTP. We present the power computations for these two extreme cases.

The tables below give the power of the test as a function of rho1, rho2, rho3 and mean number of unprotected penetrative sex occasions in the two intervention groups.

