**Table 1.**

**Power of a test for comparison of the two experimental interventions: 12 CTP sites with 10 intervention groups per site, each intervention group is of size 4.  $p = .05$**

Rho1	Rho2	Rho3	No over-dispersion			Over-dispersion		
			Mean in HE –Mean of SSB			Mean in HE –Mean of SSB		
			17-15	17-15.5	17-16	17-15	17-15.5	17-16
0.40	0.10	0.05	1.00	1.00	0.85	1.00	0.98	0.77
0.60	0.10	0.05	1.00	0.99	0.81	1.00	0.97	0.72
0.80	0.10	0.05	1.00	0.98	0.77	1.00	0.96	0.68
0.40	0.15	0.05	1.00	0.99	0.79	1.00	0.96	0.70
0.60	0.15	0.05	1.00	0.98	0.75	1.00	0.95	0.65
0.80	0.15	0.05	1.00	0.97	0.71	1.00	0.93	0.62
0.40	0.10	0.10	1.00	1.00	0.94	1.00	1.00	0.88
0.60	0.10	0.10	1.00	1.00	0.90	1.00	0.99	0.82
0.80	0.10	0.10	1.00	1.00	0.85	1.00	0.98	0.77
0.40	0.15	0.10	1.00	1.00	0.88	1.00	0.99	0.80
0.60	0.15	0.10	1.00	0.99	0.83	1.00	0.98	0.75
0.80	0.15	0.10	1.00	0.99	0.79	1.00	0.96	0.70

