## **11.5 Analytic Plan**

### **11.5.1 Testing and estimation**

All testing will be two-sided and significance will be judged at level  $\alpha=0.05$ . Effects will be reported with point estimate and 95% confidence intervals in addition to p-values.

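### Section 11.2: the over-dispersion power columns do not follow the stated variance factor, and the factor itself counts the site correlation twice; the main power conclusions are unaffected

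*Protocol*

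**What the plan says.** Section 11.2 sets the aim: "The sample size is determined to ensure sufficient power (at least 80%) of a significance test", at a level of 0.05. Section 11.5.1 adds "All testing will be two-sided and significance will be judged at level" 0.05. Three contrasts are considered: "Experimental intervention mean=15, control intervention mean=17", "Experimental intervention mean=15.5, control intervention mean=17", and 16 against 17.

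Three correlations are defined. ρ1 is between repeated measures on one woman. ρ2 is between women in the same therapeutic group. For the third the text reads "The correlation between subjects from different therapeutic groups within the same CTP (strata) is" ρ3. The constraints are ρ3 ≤ ρ2 ≤ ρ1.

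The variance is given in two forms. One is plain Poisson. The other is over-dispersed: the outcome is Poisson given cluster and stratum, and "Then the marginal variance of the outcome is over-dispersed to" 17/(1 − ρ2 − ρ3) for control, with 15 in the numerator for the experimental arm.

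Table 1 is for "12 CTP sites with 10 intervention groups per site, each intervention group is of size 4". Table 2 is for 5 groups of 8 per site, 2 on SSB and 3 on HE. Each has 12 rows of (ρ1, ρ2, ρ3) and prints power without and with over-dispersion. The text after Table 2 concludes that power is sufficient for 17 vs 15 and 17 vs 15.5. It calls power at 17 vs 16 somewhat limited, but sufficient without over-dispersion or with the larger site correlation when groups are of size 4.

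**The concern.** The stated factor depends on ρ2 and ρ3, so it must change from row to row. The printed columns behave as if it did not. Some rows with the same power before over-dispersion and different stated factors end at the same power after it.

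Separately, groups are nested in sites. Two women in one group therefore also share a site, and ρ2 already carries the site component. Subtracting ρ3 as well removes that component a second time.

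These columns are the protocol's only account of power under over-dispersion. As written, a reader cannot reproduce half of their rows from the text, and the formula in the text does not follow from the definitions beside it.

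**Working it through.** **Inputs (section 11.2; sidedness from 11.5.1).** Two-sided α = 0.05; 12 sites; two follow-up measures per woman; Table 1 with n = 4 women per group and k = 5 groups per arm per site (assumed from the balanced allocation); Table 2 with n = 8, k = 2 (SSB) and 3 (HE); no dropout.

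**Formula.** For the within-site contrast of arm means,

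Var(diff) = f × (m1/k1 + m0/k0) × c / 12, with c = (1 + ρ1)/(2n) + ((n − 1)/n)ρ2 − ρ3,

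where m1 and m0 are the arm means and f is the over-dispersion factor (1 if none). Power comes from the normal, equivalently non-central chi-square with 1 df, distribution.

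**Step 1: reproduce the plan without over-dispersion.** Table 1, (0.40, 0.10, 0.05), 17 vs 16: c = 0.175 + 0.075 − 0.05 = 0.20. Var = (16/5 + 17/5) × 0.20/12 = 0.110. The standardised difference is 1/√0.110 = 3.015, and power is 0.854 (printed 0.85). All 72 cells without over-dispersion in the two tables reproduce to rounding, within about 0.005.

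**Step 2: which f was used?** The stated factor is 1/0.85 = 1.176 for (ρ2, ρ3) = (0.10, 0.05); 1/0.80 = 1.25 for (0.15, 0.05) and (0.10, 0.10); and 1/0.75 = 1.333 for (0.15, 0.10).

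Two pairs of Table 1 rows at 17 vs 16 already show the mismatch:

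- (0.40, 0.10, 0.05) and (0.80, 0.10, 0.10) both have c = 0.20. Both print 0.85, then 0.77. The stated factors, 1.176 and 1.25, would give 0.794 and 0.769.
- (0.40, 0.15, 0.05) and (0.80, 0.15, 0.10) both have c = 0.2375. Both print 0.79, then 0.70. The stated factors, 1.25 and 1.333, would give 0.697 and 0.669.

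With f = 1.25 in every row, all 72 over-dispersed cells reproduce within 0.01 (largest gap 0.006 in Table 1, 0.009 in Table 2). With the stated factor only the 12 rows with ρ2 + ρ3 = 0.20 agree. In the other 12 the gap at 17 vs 16 runs from 1.7 to 3.3 points and exceeds 2 points in 11.

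**Step 3: which f follows from the definitions?** If ρ2 is the total correlation within a group, the variance left after conditioning on group and site is Var(X)(1 − ρ2). Hence Var(X) = mean/(1 − ρ2), with f = 1/0.90 = 1.111 or 1/0.85 = 1.176. The alternative is that ρ2 is additional to ρ3. The first row of Table 1 would then have a total within-group correlation of 0.15, so c = 0.175 + 0.1125 − 0.05 = 0.2375 and power 0.79, against the printed 0.85. The tables therefore use ρ2 as the total.

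**Results at 17 vs 16, ρ1 = 0.4:**

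| Table | ρ2, ρ3 | Printed | 1/(1 − ρ2 − ρ3) | 1/(1 − ρ2) |
|---|---|---|---|---|
| 1 | 0.10, 0.05 | 0.77 | 0.794 | 0.816 |
| 1 | 0.15, 0.05 | 0.70 | 0.697 | 0.723 |
| 1 | 0.10, 0.10 | 0.88 | 0.876 | 0.910 |
| 1 | 0.15, 0.10 | 0.80 | 0.769 | 0.819 |
| 2 | 0.10, 0.05 | 0.66 | 0.686 | 0.710 |
| 2 | 0.15, 0.05 | 0.53 | 0.532 | 0.557 |
| 2 | 0.10, 0.10 | 0.86 | 0.864 | 0.901 |
| 2 | 0.15, 0.10 | 0.68 | 0.654 | 0.708 |

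Under 1/(1 − ρ2) all 24 of the 17 vs 16 cells lie above the printed value.

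**Step 4: the main claims.** The lowest over-dispersed cell at 17 vs 15.5 is Table 2, (0.80, 0.15, 0.05): printed 0.83, 0.822 with the stated factor (which equals 1.25 in that row), 0.844 with 1/(1 − ρ2). At 17 vs 15 the same row is lowest: 0.97 printed, 0.973 and 0.979.

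**The case against.** The protocol's power program, built on a GEE quasi-score statistic, is not shown. That a constant 1.25 was applied is inferred from two-decimal output through a closed form. A few Table 2 cells miss by slightly more than rounding (0.581 against 0.59, for example). This stands as a caution about what the program did. It does not remove the mismatch: at 17 vs 16 the factors compatible with the printed pairs of powers, allowing for rounding, exclude the stated factor in all 12 discordant rows and include 1.25 in all 24.

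The tables are also a sensitivity grid over assumed correlations. Moving between neighbouring rows changes power by more than the error does (0.77 to 0.70 in Table 1, for example). That is fair, and is why the point is minor.

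Two stronger readings are tempting. A reader might infer that the double count makes half the rows wrong. It does not: the 12 of 24 come only from the mismatch with the stated formula, while the double count touches every row. A reader might also infer that power is overstated in places, because the row printed at 0.80 falls to 0.77. It falls only under the formula that is itself inconsistent with the definitions. Under 1/(1 − ρ2) that row is 0.82.

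**Conclusion.** Both defects hold and are separate. The printed over-dispersion columns contradict the stated factor in 12 of 24 rows, by about 2 to 3 points at 17 vs 16 and in both directions: too low for (0.10, 0.05), too high for (0.15, 0.10). The stated factor in turn contradicts the protocol's own definition of ρ2. Against the consistent factor, the printed 17 vs 16 powers are too low throughout, by about 2 to 5 points, so the columns err on the safe side.

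Nothing here supports a claim that the trial is underpowered. Power stays at or above 0.82 for 17 vs 15 and 17 vs 15.5 under all three factors, and the sample size of 480 does not change. The only sentence affected is the one on 17 vs 16. Of the six over-dispersed Table 1 rows with ρ3 = 0.10, three reach 0.80 as printed and four under 1/(1 − ρ2), so the blanket wording fits neither.

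The conclusion rests on five groups per arm per site in Table 1, on ρ2 as the total within-group correlation, and on the protocol's assumption of Poisson variation given group and site. The columns are conservative only within that variance model; the check does not test whether the model is realistic.

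**What to change.** In section 11.2, replace the marginal variance by mean/(1 − ρ2) and recompute the over-dispersion columns of both power tables row by row. Alternatively, keep the printed columns, state that one factor of 1.25 was used in every row, and justify it as a deliberate conservative choice. Either way, reword the 17 vs 16 sentence after Table 2 so that it names the rows that actually reach 80%. The cost is one corrected formula, one recomputation and one sentence, with no change to design, sample size or analysis.

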**Table 1.**

**Power of a test for comparison of the two experimental interventions: 12 CTP sites with 10 intervention groups per site, each intervention group is of size 4.  $p = .05$**

Rho1	Rho2	Rho3	No over-dispersion			Over-dispersion		
			Mean in HE –Mean of SSB			Mean in HE –Mean of SSB		
			17-15	17-15.5	17-16	17-15	17-15.5	17-16
0.40	0.10	0.05	1.00	1.00	0.85	1.00	0.98	0.77
0.60	0.10	0.05	1.00	0.99	0.81	1.00	0.97	0.72
0.80	0.10	0.05	1.00	0.98	0.77	1.00	0.96	0.68
0.40	0.15	0.05	1.00	0.99	0.79	1.00	0.96	0.70
0.60	0.15	0.05	1.00	0.98	0.75	1.00	0.95	0.65
0.80	0.15	0.05	1.00	0.97	0.71	1.00	0.93	0.62
0.40	0.10	0.10	1.00	1.00	0.94	1.00	1.00	0.88
0.60	0.10	0.10	1.00	1.00	0.90	1.00	0.99	0.82
0.80	0.10	0.10	1.00	1.00	0.85	1.00	0.98	0.77
0.40	0.15	0.10	1.00	1.00	0.88	1.00	0.99	0.80
0.60	0.15	0.10	1.00	0.99	0.83	1.00	0.98	0.75
0.80	0.15	0.10	1.00	0.99	0.79	1.00	0.96	0.70

**Table 2**

**Power of a test for comparison of the two experimental interventions: 12 CTP sites with 5 intervention groups per site, each intervention group is of size 8; 2 intervention groups are assigned to SSB and 3 intervention groups are assigned to HE.  $p = .05$**

Rho1	Rho2	Rho3	No over-dispersion			Over-dispersion		
			Mean in HE –Mean of SSB			Mean in HE –Mean of SSB		
			17-15	17-15.5	17-16	17-15	17-15.5	17-16
0.40	0.10	0.05	1.00	0.98	0.75	1.00	0.95	0.66
0.60	0.10	0.05	1.00	0.97	0.71	1.00	0.93	0.62
0.80	0.10	0.05	1.00	0.96	0.68	0.99	0.91	0.59
0.40	0.15	0.05	1.00	0.93	0.63	0.99	0.87	0.53
0.60	0.15	0.05	0.99	0.91	0.60	0.98	0.85	0.51
0.80	0.15	0.05	0.99	0.90	0.57	0.97	0.83	0.48
0.40	0.10	0.10	1.00	1.00	0.93	1.00	1.00	0.86

0.60	0.10	0.10	1.00	1.00	0.89	1.00	0.99	0.81
0.80	0.10	0.10	1.00	0.99	0.84	1.00	0.98	0.76
0.40	0.15	0.10	1.00	0.98	0.78	1.00	0.96	0.68
0.60	0.15	0.10	1.00	0.97	0.73	1.00	0.94	0.64
0.80	0.15	0.10	1.00	0.96	0.70	0.99	0.92	0.60

From Tables 1 and 2 above it is evident that there is sufficient power (at least 80%) to detect clinically meaningful differences between the two intervention groups with respect to number of unprotected penetrative sex occasions (difference of 17 in HE and 15 or 15.5 in the SSB) with the two extreme design situations: 10 intervention groups with 4 subjects per group and 5 intervention groups with 8 subjects per group. There is somewhat limited power when a difference of only 1 unprotected sex occasion is expected between the two interventions (17 vs. 16); although even in that case there is sufficient power when no over-dispersion is present or when the within site correlation is larger (0.1 as opposed to 0.05) and when the intervention groups are of size 4.

Notice that the higher correlation due to same CTP site ( $\rho_3$ ) the better the power. The reason for this is that the benefit of the stratification (comparing the two interventions within each CTP) offsets the negative effect of decreased number of effective degrees of freedom due to this correlation. The effect of the correlation due to same therapeutic group ( $\rho_2$ ) is only negative because the comparison of interest is not performed within a therapeutic group – this is equivalent to the detrimental effect of cluster randomization on the power. Thus, because we have each of the two treatments offered in each of the sites, the correlation due to site actually works to benefit the power. If only one of the interventions was offered in each of the CTNs, the correlation due to site would have only affected negatively the power, just as now the correlation due to therapeutic group (cluster) decreases the power.

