The design of our study – to conduct each intervention within each CTP site – makes stratification by CTP a significant source of benefit to power. This benefit strongly offsets the detrimental effect of within CTN correlation. We have made adjustments for the fact that within CTP correlation has a detrimental effect on power – by decreasing the effective degrees of freedom associated with an intervention. For example, our design calls for 20 subjects within each CTP to be assigned to each of the two interventions; the within CTP correlation decreases the 40 degrees of freedom to a number that depends on the size of the correlation. (Please note that the group nature of the intervention is another source of decrease in degrees of effective freedom – due to correlation within group). These conditions have been taken into account in the sample size computations. In fact, the larger the within CTP correlation, the better the power is. Stratification by CTP results in a more powerful test – much like the paired t-

test is more powerful than the two-sample t-test when pairs of observations are known to be associated. (The pairs of observations in this study are the means of the outcome for the experimental and control interventions within CTP site). Sample size computations are performed using the exact model that will be used in the analysis. These computations take into account both the (relatively small) detrimental effect of within CTP correlation and its (relatively large) beneficial effect. The interaction between site and intervention effect is treated as random effect with variance  $\sigma^2$ .

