#### **11.5.7 Missing data and dropout**

We will make any effort to assess all subjects at both follow-up times (3- and 6-months post-intervention). Despite our thorough and proactive approach to taking complete measurements on all randomized study subjects at all time points, we expect that there will be cases when assessments will be incomplete or missing. The analytic strategy in such cases will depend on the nature of the missing pattern and missing data. For example if at a given assessment time a subject has all but a few items of a questionnaire, a prorated score based on the available items will be computed. As another example, when data on a subject are available only at baseline, such subject

cannot be included in the analysis since even the modern statistical methods like Longitudinal Models (described above) require observations on at least two occasions; in such case some imputation is needed for values of the outcome at follow-up. In general, we will use multiple imputation approach based on propensity scores (Lavori et al., 1995). However, for some outcome measures alternative imputation methods might be more appropriate; for example, for the dichotomous secondary outcome measure 'taking condoms from open clinic supplies' it will be more appropriate to impute 'no' for the missing value of subjects who can not be brought to the clinic for assessment.

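### The claim of at least 80% power for 17 vs 15 or 15.5 occasions is not supported: the variance is Poisson (SD about 4) and leaves out differences between women

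*Protocol*

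**What the plan says.** Protocol section 11.2 sizes the trial at 12 sites of 40 women (480 in all) for at least 80% power at alpha 0.05; section 11.5.1 makes all tests two-sided. The power method is a GEE quasi-score test: "In the analysis we assume the outcome (the number of unprotected sex occasions) follows a Poisson distribution". The variance is not taken from data: "The variance parameters are determined by the means described above, since the outcomes are Poisson random variables". A second set of columns, headed over-dispersion, divides that variance by 1-rho2-rho3, which adds variation between therapy groups and between sites only.

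The grid is rho1 (within woman) 0.4, 0.6, 0.8; rho2 (within group) 0.10, 0.15; rho3 (within site) 0.05, 0.10. Power Table 1 has ten groups of 4 per site. Power Table 2 has five groups of 8 (2 SSB, 3 HE). Printed power is 0.97-1.00 for 17 vs 15 and 0.83-1.00 for 17 vs 15.5. The text after Table 2 concludes that "it is evident that there is sufficient power (at least 80%) to detect clinically meaningful differences between the two intervention groups".

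The mean of 17 comes from a cited trial, for which the section also gives unpublished arm averages: "Baseline: Control (0 intervention sessions):17.4; 4-session intervention: 13.7; 8-session intervention: 20.9". No SD or arm size from that trial is reported.

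**The concern.** Three-month counts of sexual occasions can be expected to differ between women for lasting reasons, such as whether they have a regular partner. A variance equal to the mean treats women as nearly interchangeable. The over-dispersion option does not repair this, because it covers only group and site.

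This calculation is the stated justification for 480 women. If the variance is too small, the power is too high, and a null result could be read against a claimed power near 1 that the design has not been shown to have.

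**Working it through.** **1. Reproducing the tables.** Let V be the variance of one count, m the group size and g the number of groups per arm per site. With two follow-up visits, the variance of an arm mean within a site is V·f(g), where

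f(g) = [1 + rho1 + 2(m-1)rho2 + 2m(g-1)rho3] / (2mg).

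The variance of the arm difference is [V_HE·f(g_HE) + V_SSB·f(g_SSB) - 2·rho3·sqrt(V_HE·V_SSB)] / 12. Power is for a two-sided 0.05 test. The protocol does not print a formula; this one was chosen because, with V = mean, it returns all 72 cells without over-dispersion to within 0.01.

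Example: Table 2, row 0.80/0.15/0.05, 17 vs 15.
- f(3) = (1.8 + 2.1 + 1.6)/48 = 0.1146; f(2) = (1.8 + 2.1 + 0.8)/32 = 0.1469.
- Variance = (17×0.1146 + 15×0.1469 - 0.10×sqrt(255))/12 = 0.213; SE = 0.461.
- z = 2/0.461 = 4.34; power 0.99, as printed.

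**2. SDs used.** sqrt(17) = 4.12. The largest over-dispersed value is sqrt(17/0.75) = 4.76.

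**3. Check against the cited baseline means.** Before treatment, randomised arms share one expected mean. The three means average 17.33 and their squared deviations sum to 25.93. With n women per arm, the 2-df heterogeneity statistic is n×25.93/V.
- V = 17.33 (Poisson): 1.50n. It exceeds 5.99 from n = 5 (p = 0.024).
- V = 17.33/0.75 (largest over-dispersion): 1.12n. It exceeds 5.99 from n = 6 (p = 0.035).

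Arm sizes are not given, but the rejection needs only these few women per arm.

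**4. Check against the protocol's own rho1.** If a woman's counts are Poisson about her own stable rate, the covariance between visits is the between-woman variance of that rate. Then rho1 = (V - mean)/V, so V = mean/(1-rho1). Conversely, keeping V = 17 with rho1 = 0.8 leaves a within-woman variance of 17×0.2 = 3.4 for a mean of 17, far below Poisson.

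Substituting V = mean/(1-rho1) into step 1 (no baseline adjustment; ranges over rho2, rho3 and both group sizes):

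| rho1 | SD at mean 17 | 17 vs 15 | 17 vs 15.5 |
|---|---|---|---|
| 0.4 | 5.3 | 0.95-1.00 | 0.76-0.98 |
| 0.6 | 6.5 | 0.81-0.98 | 0.56-0.87 |
| 0.8 | 9.2 | 0.49-0.78 | 0.30-0.53 |

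In the example row, V rises fivefold, so SE = 0.461×sqrt(5) = 1.03, z = 1.94 and power = 0.49.

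**5. Illustrations at assumed SDs** (same formula and grid, equal SD in both arms, no baseline adjustment). These SDs have no source in the protocol.

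| SD | 17 vs 15 | 17 vs 15.5 |
|---|---|---|
| 10 | 0.41-0.81 | 0.25-0.56 |
| 15 | 0.21-0.47 | 0.14-0.29 |
| 20 | 0.14-0.29 | 0.10-0.19 |

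Steps 4 and 5 hold rho2 and rho3 fixed, so group and site variance grow with V.

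**6. Over-dispersion columns (minor).** The stated factor 1/(1-rho2-rho3) runs from 1/0.85 = 1.18 to 1/0.75 = 1.33. One fixed factor, 1/0.80 = 1.25, returns every printed cell to within 0.01. For Table 1, 17 vs 16, row 0.40/0.10/0.05 prints 0.77 where the stated formula gives 0.79; row 0.40/0.15/0.10 prints 0.80 where it gives 0.77.

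**The case against.** **Baseline adjustment.** This is the strongest objection. Model (1) in section 11.6.1 includes the baseline count, and neither the printed tables nor steps 4 and 5 credit it. As a linear approximation, give baseline a correlation of rho1 with both visits: (1+rho1)/2 becomes (1+rho1)/2 - rho1² in the between-woman term, with the rho2 and rho3 terms unchanged. At rho1 = 0.8 this falls from 0.90 to 0.26. In the example row:
- f(3) = (0.52 + 2.1 + 1.6)/48 = 0.0879; f(2) = (0.52 + 2.1 + 0.8)/32 = 0.1069.
- With V = 85 and 75, SE = 0.79, z = 2.53 and power = 0.72 instead of 0.49.

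On the same basis, power for 17 vs 15 at SD 10 becomes 0.50-1.00 instead of 0.41-0.81. The objection stands in part: the unadjusted ranges are not those of the planned analysis. Some scenarios then pass 80% and others do not.

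**Unknown SD.** This also stands. A reader might infer that the power claim is false, or read an SD off the three cited means. The documents support neither. Arm sizes are missing, and three means (2 df) estimate an SD poorly. Taking only the widest gap between arms would suggest that rejection needs fewer women, but the test on all three means does not reject at 3 or 4 per arm (p = 0.11 and 0.050).

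**Larger effects.** The cited trial's 3-month means (19.5 vs 13.17 and 11.23) differ by more than 2, so a larger true effect may be detectable. The point concerns only 17 vs 15 or 15.5.

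**Other readings the documents do not support.**
- Section 11.5.4 says "Sample size computations are performed using the exact model that will be used in the analysis" and mentions a random site-by-intervention term. A reader might conclude that the power calculation wrongly omits that variance. The term belongs to linear mixed model (2) for continuous outcomes; the primary count uses marginal GEE model (1), which has none.
- A reader might expect the interim futility rule to inherit the design variance. Section 11.8 conditions on the interim data and does not refer to it.
- The over-dispersion slip does not overturn the claim. Under the stated formula, 17 vs 15.5 stays at 0.82 or above.
- The tables assume complete data, although section 11.5.7 says "we expect that there will be cases when assessments will be incomplete or missing". With Poisson variance and an assumed 80% retention, 17 vs 15.5 stays at 0.86 or above. Retention belongs in the recalculation but is not the fault.

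**Conclusion.** The claim of at least 80% power for 17 vs 15 or 15.5 is not supported as written. The table arithmetic without over-dispersion is sound; the variance input is the fault, and two of the protocol's own inputs contradict it. The rejection from the cited means assumes only 5 women per arm (6 for the largest over-dispersed variance). The rho1 argument needs no outside figure, but it assumes Poisson counts given the woman and a stable rate across visits. On that basis, without baseline adjustment:
- 17 vs 15 keeps 80% power throughout at rho1 = 0.4 and 0.6, and loses it in every scenario at rho1 = 0.8;
- 17 vs 15.5 falls below 80% in at least some scenarios at every rho1, and in all of them at 0.8.

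How far true power falls short, if it does, depends on an SD the protocol does not give and on the gain from the baseline covariate. The mismatch in the over-dispersion columns is a reporting error only.

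**What to change.** In section 11.2:
- Recompute power Tables 1 and 2 with a variance that includes between-woman variation (negative binomial, or an empirical SD), shown over a range such as SD 10, 15 and 20.
- Include expected retention, and credit the baseline covariate in model (1) with its assumed correlation stated.
- State the over-dispersion factor actually used, or correct the columns to the stated formula.
- Replace the 80% statement with the difference detectable at N = 480 under each assumption.
- Check the SD on pooled baseline data, blind to arm.

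The cost is a rewritten section and probably a less favourable power statement. The sample size, outcome and primary analysis do not change.
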